The incidence of supraventricular arrhythmias is between 8 - 35% (6-11) and considerably lower for ventricular arrhythmias (5;10-14). Cardiac parameters, such as right ventricular diameter, right ventricular longitudinal dimension and right atrial length, significantly correlate with an increased risk of arrhythmias (7). Supraventricular tachycardias (SVT) may compromise cardiac function and worsen the prognosis of patients with PAH (6), but information about their incidence and clinical role is based on a small number of retrospective studies (5;6;10;11;15). Additionally, permanent atrial fibrillation and prolonged QTc interval are associated with the highest mortality (16). The goal in management of arrhythmias is to maintain sinus rhythm either by pharmacological or device treatment.

This research project is the first study applying continuous long-term monitoring of arrhythmias in patients with PAH and right heart failure (RHF). The study specifically seeks to investigate following:

- The incidence and type of supraventricular and ventricular arrhythmias in PAH by continuous long-term monitoring
- The predictive value of both right and left ventricular cardiac magnetic resonance (CMR) imaging parameters for arrhythmogenesis in PAH.
- Optimization of specific therapy in PAH using continuous long-term arrhythmia monitoring

Project ASPIRE I:

Incidence and characteristics of supraventricular and ventricular arrhythmias in PAH

Background

A. Supraventricular arrhythmias

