Study design	Single centre observational study with CMR and insertable cardiac long term monitoring in newly referred and PAH patients treated with PAH-specific therapy. Patients will be followed for 2 years after inclusion.
Study objectives	Primary objective To evaluate CMR as a tool for providing noninvasive predictors for arrhythmias in patients with PAH. Secondary objectives

ASPIRE: ArrhythmiaS in Pulmonary arterial hYPERtension and right heart failure assessed by continuous long-term cardiac monitoring

	
 - To assess change in 6 MWT - To assess hemodynamic changes with RHC - To assess hemodynamic changes in echocardiography - To assess the number of patients progressing one FC (Modified NYHA class) - To assess changes in NT-proBNP. - To assess Hospital admission for any reason - To assess Death or transplantation
Methodology	The study will be conducted as a single center study at Copenhagen University Hospital, Rigshospitalet, DK-Denmark.
Trial duration	Enrollment duration: 9 months
Number of patients	40 patients. WHO Group I PAH: 10 with IPAH, 10 with CTD-aPAH, WHO Group III : 10 with pulmonary disease related PH and Group IV: 10 with CTEPH.
Selection criteria	
Inclusion criteria:
 
The following patients will be included in the study:
 
 - Patients >18 years of age - Voluntary participation after giving informed verbal and written consent - Patients untreated with PAH specific therapy - Patients on current PAH specific medication independent of duration of therapy - Patients can be in WHO group 1 only with IPAH or CTD-aPAH, and group IV, CTEPH 
Exclusion Criteria
 
 - Patients who are unlikely to comply with the study protocol and procedures required by the study protocol. - Patients with any severe complication or comorbidity other than PAH which might determine the prognosis and functional level of the patient. - Renal insufficiency (GFR estimated <60 ml/min/ 1.73 m²). - Implanted ferromagnetic metal parts unsuited for CMR (ICD, cerebral clips) - Claustrophobia - Allergy or hypersensitivity to Gadovist 
Concomitant treatments
 
 - Patients can be on the following treatments only if they have been at least treated for three months prior to inclusion and are planned to be continued during the whole study period: diuretics, digoxin, beta-blockers, amiodarone

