Data collection	
At screening:
 
 - SPECT/CT will be performed at diagnosis for prevalent cases only and at screening for incident cases to evaluate pulmonary embolism - LFT to exclude pulmonary disease: COPD and ILD - Echocardiography to exclude left heart disease - PAH verified with right heart catheterization before start of PAH specific medication - Basic demographic data including medication. - Physical examination and vital signs - 6 MWT - ECG - Lab tests including liver and renal function tests and NT-pro-BNP 
Visits every 6 months or with increased symptomatology
 
 - CMR with measurement of RV/LV volumes, CI (volumetric and flow), RVEF and pulmonary artery diameter according to standard criteria. Yearly measurement of RV fibrosis (LGE, T1 mapping and ECV). The same MR-scanner must be used for all measurements.

ASPIRE: ArrhythmiaS in Pulmonary arterial hYPERtension and right heart failure assessed by continuous long-term cardiac monitoring

	
 - 6 MWT - Lab tests, including liver and renal function tests including yearly eGFR, hematocrit and NT-proBNP - Echocardiography yearly and at 3 month after inclusion - Record concomitant medications - PAH medications
Endpoints	
Coprimary endpoints
 
 - Change in cardiac index, right atrial size, RV size, fibrosis and stroke volume - Arrhythmias as assessed by Insertable Cardiac Monitors 
Secondary endpoints
 
 - Modified NYHA functional class - Reduction in 6 MWT in the study period. - NT-proBNP change in study period. - Change and /or escalation of PAH therapy - Respiratory hospitalization - Death or transplantation

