Statistical methods	
Repeated measurements of CI, right atrial size, RV size, fibrosis and stroke volume will be performed every 6 months.
 
Two groups of subjects will be defined: 1. Patients with no change in CI, RV size and stroke volume, and 2. A group of patients where one of the measurement change more than 2 standard deviations.
 
It is group-shift (Y/N) if a subject changes out of the 2 stdv band.
 
Time to group shift will be analysed in a subsequent analysis.
 
Cox-model analysis will be done on measurements of (1) cardiac index, (2) RV size, (3) stroke volume and (4) fibrosis to calculate the correlation with risk of developing clinical symptoms and clinical deterioration. In other words, this analysis will establish if the MR-measurements predict clinical outcome.
 
SPSS/PASW Statistics 19 software (SPSS Inc, Chicago IL), SAS or R is used for all statistical analysis.

MRI protocol

Every six months, all subjects are scanned according to the protocol below. The scanning will take 60-80 minutes. MRI scans will be carried out on a 1.5 to 3.0 Tesla MRI scanner. At visit 1, 3 and 5 a cannula will be placed for contrast administration.

MRI studies will provide time-volume curves for LV and RVs filling and ejection fraction, peak emptying rate, peak filling rate and stroke volume will be calculated.

The measurements will provide time-flow curves for flow in the pulmonary trunk, pulmonary branch arteries and aorta. It will be possible to measure the distribution of flow to the right and left lung. Since the pulmonary trunk is often dilated with slow flow, it can be more accurately to measure the flow in the smaller branch pulmonary arteries.

Angiography will also provide the flow distribution in the lungs and the different segments of the lungs.

After baseline scan subjects will be exercised by a MR compatible ergometer with a load of 1 watt per kg. Stress test will measure the physiological reserve in terms of changes in cardiac index and ventricular volumes. Finally, late enhancement will measure the degree of fibrosis in the left and right ventricle.

Scannings protocol		Sekvens
1	Scout	SSFP, single shot
2	Transverse stack, no gaps – covers the hearts	SSFP, 8 mm, 25 phases

ASPIRE: ArrhythmiaS in Pulmonary arterial hypertension and right heart failure assessed by continuous long-term cardiac monitoring

3	LV vertical long axis (VLA)	SSFP, 8 mm, 25 phases
4	Scout LV, short axis	SSFP, single shot

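### ASPIRE II sets out to predict arrhythmia from CMR, but its statistical methods name no analysis with arrhythmia as the outcome, and right atrial size is missing from the Cox list

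*Combined protocol and SAP*

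**What the plan says.** The list of aims in the introduction includes "The predictive value of both right and left ventricular cardiac magnetic resonance (CMR) imaging parameters for arrhythmogenesis in PAH". The ASPIRE II synopsis gives the primary objective as "To evaluate CMR as a tool for providing noninvasive predictors for arrhythmias in patients with PAH". Its Endpoints row has two coprimary entries: "Change in cardiac index, right atrial size, RV size, fibrosis and stroke volume" and "Arrhythmias as assessed by Insertable Cardiac Monitors".

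The Statistical methods row of the same synopsis contains:

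- A measurement schedule: "Repeated measurements of CI, right atrial size, RV size, fibrosis and stroke volume will be performed every 6 months".
- A split into two groups. Group 1 is "Patients with no change in CI, RV size and stroke volume". Group 2 is patients in whom one measurement moves by more than two standard deviations. The purpose of the split is not stated, except that "Time to group shift will be analysed in a subsequent analysis".
- A Cox analysis of cardiac index, RV size, stroke volume and fibrosis "to calculate the correlation with risk of developing clinical symptoms and clinical deterioration". The next sentence describes this as showing whether the MR measurements predict clinical outcome.

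The word arrhythmia does not occur in that row.

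**The concern.** The objective and one coprimary endpoint point to arrhythmia, while the one regression model in the plan points to clinical course. A patient may have a monitor-detected arrhythmia without symptoms, or may deteriorate without arrhythmia. A model of clinical deterioration therefore need not give the same answer as a model of arrhythmia. An analyst who follows the text could complete every stated analysis and still have no estimate of the association between CMR and arrhythmia.

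An arrhythmia analysis would presumably be added later. Its event definition, time origin and choice of predictors would then be made after the data were available, because nothing in the plan fixes them.

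The omission of right atrial size adds to this. The protocol's own background treats right atrial dimensions as candidate markers of arrhythmia risk, yet the Cox list leaves the measure out.

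**Working it through.** The plan states no alpha, power or sample-size derivation for ASPIRE II, so there is no figure to reproduce. The check is a comparison of the text.

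**Step 1: outcomes.** The Statistical methods row names two analysed outcomes: group shift, which is a change in CMR measures, and clinical symptoms or deterioration. Arrhythmia is neither: 0 of 2.

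**Step 2: other places that could fill the gap.** Apart from software, the ASPIRE I Statistical methods row covers heart rate variability and heart rate only. The ASPIRE III row names software only. Neither states an analysis of CMR against arrhythmia.

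**Step 3: are the two outcomes the same event?** The Endpoints row lists arrhythmia separately from functional class, walk test, NT-proBNP, therapy escalation, hospitalization, and death or transplantation. The section on the CareLink network gives silent atrial fibrillation as an example of what remote monitoring should pick up. Such an episode is an arrhythmia but not, in itself, a clinical symptom.

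**Step 4: where each coprimary CMR measure appears.**

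| Measure | Repeated measurements | Named in group 1 | Cox list |
|---|---|---|---|
| Cardiac index | yes | yes | yes |
| RV size | yes | yes | yes |
| Stroke volume | yes | yes | yes |
| Fibrosis | yes | no | yes |
| Right atrial size | yes | no | no |

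Group 1 names 3 of 5 and the Cox list names 4 of 5. Right atrial size is the only measure in neither. Table 1 in the ASPIRE II background lists three right atrial measures among the risk factors for supraventricular arrhythmia (SVA), with hazard ratios of 1.80 (diameter), 2.08 (length) and 1.07 (area). That table is univariate, from echocardiography, in IPAH. Its largest hazard ratio is 2.76, for RV diameter, and RV size is in the Cox list.

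**Step 5: precision of an arrhythmia model (illustration only).** Assume that the background SVA figures apply to 40 patients over two years.

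- 2.8% per year: 40 × (1 − exp(−2 × 0.028)) = 2.2 patients
- 8.4%: 40 × 0.084 = 3.4
- 15%: 40 × 0.15 = 6
- 20%: 40 × 0.20 = 8
- 35%: 40 × 0.35 = 14

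For one standardised predictor and d events, the standard error of the log hazard ratio is about 1/√d, so the 95% limits are the estimate divided and multiplied by exp(1.96/√d).

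- d = 8: exp(1.96/2.83) = 2.0
- d = 14: exp(1.96/3.74) = 1.7

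Simulated 40-patient Cox fits with no association gave median factors of 2.1 and 1.7. At 2 or 3 events the approximation is unreliable, so no interval is given. These counts cover SVA only, whereas the coprimary endpoint is arrhythmia without restriction. The cited figures come from differing follow-up periods, and the cohort behind the 2.8% had no continuous recorders. The true number could be higher.

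**The case against.** The strongest reply is that the protocol itself ties arrhythmia to clinical course. The ASPIRE II background says arrhythmia often leads to deterioration and, in describing a study of transposition of the great arteries, counts arrhythmia among adverse clinical outcomes. The ASPIRE III background relates the onset of atrial tachyarrhythmia to deterioration in most cases. On that view, clinical outcome in the Cox sentence may already include arrhythmia, and the two-group split may be meant for comparing arrhythmia between groups.

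Much of this stands. A reader might infer that the protocol treats arrhythmia and clinical course as unrelated, or that a silent episode would certainly not count as an event in the Cox model. The documents support neither: the link is stated more than once, and an undefined outcome cannot be said to exclude anything for certain. But a usual association is not identity, and a possible reading is not a stated analysis of the primary question.

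On right atrial size, the group 2 wording follows a list of all five repeated measures and can be read to cover them. A reader should therefore not infer that right atrial size is excluded from the group analysis altogether. What stands is that group 1 does not name it and the Cox list omits it.

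A reader might also see a conflict in the contrast visits, numbered 1, 3 and 5, and conclude that fibrosis has no baseline value. The ASPIRE II chart marks the scans at implantation, 12 and 24 months with a distinct symbol. These are the first, third and fifth scans, which agrees with yearly fibrosis measurement. At most the labels need clarifying.

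Finally, one could measure the defect by the false-positive risk of testing several CMR measures. That would be misplaced: no alpha is stated, and the remedy still examines five measures, so the risk would be unchanged. Only the labelling and completeness of reporting improve.

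**Conclusion.** The point holds. The ASPIRE II methods name no analysis with arrhythmia as the outcome, although arrhythmia is the subject of the primary objective and a coprimary endpoint. The stated Cox outcome is undefined and does not name it. Unless that outcome is read to include arrhythmia, the stated model does not answer the primary question. Right atrial size is absent from the Cox list, which covers 4 of the 5 coprimary measures.

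This is more than missing detail, because the model that is specified is directed at another outcome. The conclusion rests on the text alone. The event counts are assumptions and bear only on how precise an added model could be. The gap should be closed before CMR and monitor data are linked.

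**What to change.** Add to the ASPIRE II Statistical methods, ahead of the present Cox sentence:

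> *Primary analysis: cause-specific Cox model for time from ICM insertion to first qualifying ICM-detected arrhythmia, with death or transplantation as a competing event (censored). Qualifying arrhythmia types and minimum duration are fixed in writing before CMR and ICM data are linked. Baseline cardiac index, right atrial size, RV size, stroke volume and fibrosis are entered one at a time, and all five hazard ratios are reported with 95% confidence intervals, as exploratory. Time-updated values (latest scan before the event) are a secondary analysis.*

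Monitor insertion suits as time origin because the ASPIRE II chart places the first CMR there. Baseline values come first because a change can predict only arrhythmia that begins after the scan that shows it; the time-updated analysis serves the coprimary endpoint on change.

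State also how patients with prior arrhythmia are handled in the analysis. ASPIRE I excludes patients already treated for arrhythmia, ASPIRE II lists no such exclusion, and both permit amiodarone.

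Keep the clinical-deterioration Cox model as secondary, with its event tied to the clinical endpoints already listed in the ASPIRE II Endpoints row.

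The cost is protocol wording, one agreed arrhythmia definition and a little more analysis work. The data are already planned. The drawback is imprecise estimates, since arrhythmia events may be few in 40 patients; hence one predictor per model and the exploratory label.

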5	The four standard views (4 chamber, 3 chamber, 2 chamber, LVOT coronal)	SSFP, 8 mm, 25 phases
6	LV short axis stack, no gaps	SSFP, 8 mm, 25 phases
7	RV long axis	SSFP, 8 mm, 25 phases
8	RV inlet-apex-outlet (3 points)	SSFP, 8 mm, 25 phases
9	RVOT – PA x 2 perpendicular views	SSFP, 8 mm, 25 phases
10	RVOT short axis	SSFP, 8 mm, 25 phases
11	Left pulmonary artery x 2 perpendicular	SSFP, 8 mm, 25 phases
12	Left pulmonary artery short axis	SSFP, 8 mm, 25 phases
13	Right pulmonary artery x 2 perpendicular	SSFP, 8 mm, 25 phases
14	Right pulmonary artery short axis	SSFP, 8 mm, 25 phases
15	Pre-contrast T1-mapping 4ch Pre-contrast T1-mapping short-axis T2-mapping 4ch T2-mapping short-axis	
	*Kontrast injection: Gadovist 1.5 mmol/kg	
16	*Rest myocardial perfusion scan	
17	PA flow	Velocity encoding, VENC 10 % above max velocity
18	LPA flow	Velocity encoding, VENC 10 % above max velocity
19	RPA flow	Velocity encoding, VENC 10 % above max velocity
20	Aorta flow	Velocity encoding, VENC 10 % above max velocity
	Post-contrast T1-mapping 4ch Post-contrast T1-mapping short-axis	
21	*Late enhancement LV short axis stack	Inversion recovery, FLASH
	Stress 1 watt/kg	
22	Transverse stack, no gaps – cover the heart	SSFP, 8 mm, 25 phases
23	PA flow	Velocity encoding, VENC 10 % above max velocity
24	Aorta flow	Velocity encoding, VENC 10 % above max velocity
25	LV short axis stack, no gaps	SSFP, 8 mm, 25 phases

* Contrast studies will only be performed at visit 1, 3 and 5.

LV: left ventricle, LVOT left ventricular outflow tract, RV, right ventricle, PA, pulmonary artery, LPA. Left pulmonary artery, RPA, right pulmonary artery.

Study Chart – ASPIRE II

	Screening	ILR implantation	Visit 1	Visit 2	Visit 3	Visit 4
		1	6 mo	12 mo	18 mo	24 mo
Informed consent	X					
Height	X					
Weight	X					
RHC [✉]	X					
SPECT/CT	X					

ASPIRE: ArrhythmiaS in Pulmonary arterial hYPERtension and right heart failure assessed by continuous long-term cardiac monitoring

LFT	X					
ECG	X	x	X	X	x	X
Echocardiography	X			x		x
6 MWT	X	X	X	X	x	X
Clinical data collection	x	X	X	X	X	X
CMR		X§	x	X§	x	X§
Blood Samples#	X	x	X	x	x	x

¤ RHC: right heart catheterisation for incident cases only. Prevalent cases have had RHC at the time of diagnosis. *CMR, cardiac index, RV size, stroke volume and pulmonary artery diameter including exercise measurements #Blood samples include haematology, liver chemistry (ALT, AST, LDH bilirubin) renal (creatinine, eGFR), and NT-proBNP.

Project ASPIRE III

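### Safety query: the only contrast dose in ASPIRE II, Gadovist 1.5 mmol/kg, has nothing in the plan to check it against and implies an implausibly large volume; verify it before any contrast scan.

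*Combined protocol and SAP*

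**What the plan says.** The dose is in the scan table of the MRI protocol section of Project ASPIRE II, on an unnumbered line between pre-contrast mapping (row 15) and rest perfusion (row 16): "Kontrast injection: Gadovist 1.5 mmol/kg". Post-contrast T1 mapping and late enhancement follow further down the table. No second contrast line appears.

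On timing, the table footnote says "Contrast studies will only be performed at visit 1, 3 and 5", and the text above the table says "At visit 1, 3 and 5 a cannula will be placed for contrast administration". The Study Chart for ASPIRE II numbers its visits only up to 4 (24 months). It marks CMR with § at implantation, 12 months and 24 months.

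Contrast comes up in two other places, neither with an amount:
- The ASPIRE II exclusion criteria bar patients with an estimated GFR below 60 or with hypersensitivity to the product.
- The MR scan text under Risks and side effects describes yearly contrast, lists side effects, and withdraws contrast if kidney function falls.

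The planned sample is "40 patients. WHO Group I PAH: 10 with IPAH, 10 with CTD-aPAH", with 10 patients each from WHO Groups III and IV making up the rest. Contrast feeds part of the fibrosis assessment, described as "Yearly measurement of RV fibrosis (LGE, T1 mapping and ECV". Fibrosis belongs to the first coprimary endpoint: "Change in cardiac index, right atrial size, RV size, fibrosis and stroke volume".

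**The concern.** A dose per kilogram is an operative instruction: someone multiplies it by a weight and injects the result. Here the multiplication gives a volume that looks too large for one contrast line placed immediately before a perfusion scan. That pattern suggests a misplaced decimal or a wrong unit.

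Nothing in the plan would expose such a slip. The renal and allergy exclusions and the stopping rule decide who receives contrast, not how much. The risk text names no amount that could be compared with the table.

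If the figure is wrong and is followed, patients with pulmonary hypertension are exposed to the error at up to three scans each. If it is wrong and the imaging unit gives its usual amount instead, the protocol has no record of the dose behind the contrast-dependent fibrosis measurements.

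**Working it through.** **Inputs from the documents**
- Dose: 1.5 mmol/kg (scan table).
- Contrast scans per patient: 3 (scan table footnote).
- Patients: 40 (Study Synopsis, ASPIRE II).

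**Assumed inputs, not in the documents**
- Body weight: 70 kg, with a range of 50-100 kg.
- Product concentration: 1.0 to 0.5 mmol/mL.
- Injection rate, used only in step 3: 3-5 mL/s.

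The plan does not derive the 1.5 mmol/kg, so there is no calculation of its own to reproduce.

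**Step 1: amount per contrast scan.** mmol = dose x weight. At 70 kg: 1.5 x 70 = 105 mmol.

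**Step 2: volume per contrast scan.** mL = mmol / concentration. At 70 kg: 105 / 1.0 = 105 mL and 105 / 0.5 = 210 mL.

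**Step 3: injection time.** Shortest = smallest volume / 5; longest = largest volume / 3. At 70 kg: 105 / 5 = 21 s and 210 / 3 = 70 s.

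| Weight (assumed) | Amount | Volume at 1.0-0.5 mmol/mL | Time at 3-5 mL/s |
|---|---|---|---|
| 50 kg | 75 mmol | 75-150 mL | 15-50 s |
| 70 kg | 105 mmol | 105-210 mL | 21-70 s |
| 100 kg | 150 mmol | 150-300 mL | 30-100 s |

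The times bear only on whether the amount suits rest perfusion. That scan is not an endpoint, and the times say nothing about mapping or late enhancement, which come after the flow sequences in rows 17-20.

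**Step 4: exposure over the study.** Per patient: 3 x 1.5 = 4.5 mmol/kg. At 70 kg this is 3 x 105 = 315 mmol, or 315-630 mL. Number of contrast scans: 40 x 3 = 120. This is a ceiling, since deaths, transplantation and the kidney-function rule will reduce it.

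**Step 5: would a simple slip explain the volume?** For illustration only, at 70 kg:
- A tenfold decimal slip: 0.15 x 70 = 10.5 mmol, or 10.5-21 mL.
- A unit meant as mL/kg: 1.5 x 70 = 105 mL, which leaves the volume as large as before.

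The two slips lead to different places, and the documents do not point to either.

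**Step 6: visit labels.** Read literally against the chart, visits 1 and 3 are the 6- and 18-month visits, and visit 5 does not exist. Read as the first, third and fifth CMR, the labels give implantation, 12 and 24 months. This matches the § marks and the yearly contrast in the risk text, so it is the reading used here.

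**The case against.** The strongest objection is that no error has been shown. No line contradicts 1.5 mmol/kg, and no calculation in the plan fails. Weight, concentration and injection rate all come from outside, and so does the judgement that the volume is too large, because the documents give no usual volume or maximum. The table does not say whether the contrast is given as one bolus. The MRI protocol text also mentions angiography, which has no row in the table and might account for a larger amount. The text was machine-read from a PDF, so a digit or decimal point may have been lost, and that would not be an error in the plan.

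All of this stands. It limits the point to a query. It does not remove the query, because the line is a drug dose that the plan gives no means of checking.

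A reader might also infer that the dose damages the fibrosis endpoint through late enhancement and ECV. The documents do not support that as a demonstrated harm. Any such effect would depend on relaxation properties that the plan does not give. It would also depend on the delay after injection, which is unsettled: the text puts late enhancement after exercise ("Finally, late enhancement will measure the degree of fibrosis in the left and right ventricle"), while the table lists "Late enhancement LV short axis stack" at row 21, before stress.

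On weight, the chart lists it only at screening. However, clinical data collection is charted at every visit, and the exercise load is set per kilogram, so staff will probably have a current weight. Recording it with the dose is good practice rather than the correction of a shown fault.

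**Conclusion.** The point holds as a safety query. The only contrast dose in the documents is given without concentration, volume, maximum or source. It implies 105 mmol per contrast scan at an assumed 70 kg, which is 105-210 mL at an assumed 1.0-0.5 mmol/mL, or 75-300 mL over 50-100 kg. That looks implausibly large where the line stands. It applies to up to three contrast scans per patient, at most 120 in total.

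A reader might infer that the plan contains a proven tenfold overdose, or a failed calculation. The documents support neither. They cannot show whether the figure is wrong, or whether an error would lie in the decimal, the unit or the reading of the PDF. No replacement dose can be derived from them, and none is proposed.

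The arithmetic is certain given its inputs. The suspicion rests on the assumed weight and concentration and on a judgement about plausible volume. Verification should still come before any contrast scan, because it is cheap and an unverified drug dose should not be followed.

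**What to change.** Before any contrast scan, the sponsor should:

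1. Check the figure and unit in the source file, to rule out a text-reading error.
2. Check them against the product labelling and the imaging unit's written procedure.
3. If the figure is wrong, amend the line to the verified mmol/kg dose, with the product concentration and the resulting mL/kg. If it is right, keep it and add the concentration, mL/kg and source.
4. In either case, record the weight used and the amount given at each contrast scan, so that late enhancement and ECV are compared at a known dose.
5. Reword the contrast visits to match the chart: implantation, 12 and 24 months.

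The check takes a few minutes. A wrong figure needs a one-line amendment with ethics notification. Recording needs one or two case-report fields. No extra patients or procedures are involved.
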